15.10. Study Workflow

See Section 15.1.10. Study Workflow.

15.11. Target Sample Size and Period

The enrollment target for the translational study is 80% to 90% of the patients enrolled in the main study. The enrollment period will be the same as that for the main study.

15.12. Potential Benefits and Risks/Discomforts for Patients

Potential benefits

Identification of protein or gene biomarkers that could predict response to standard sorafenib-based treatment for hepatocellular carcinoma could be used for treatment stratification by biomarkers and would make a major contribution to the future treatment of hepatocellular carcinoma. No useful biomarker for angiogenesis inhibitors has yet been found, and thus this discovery could also contribute biomarkers for various other angiogenesis inhibitors.

Potential risks/discomforts for patients

Risks and discomforts associated with the translational study should be minor, as the study only requires blood sampling (peripheral blood, total volume of 12 mL) and collection of a tumor tissue specimen by liver biopsy (ultrasound-guided needle biopsy), which is commonly performed in routine care. There is an extremely small risk of serious complications associated with hemorrhage and other issues with liver biopsy, and thus the procedure will be performed with the informed consent of the patient. Due care will be taken to prevent and manage complications from liver biopsy.

Risks related to patient rights and privacy are also very low because (1) the study will be conducted with the full informed consent of the patient in accordance with the study protocol, (2) personal information will be anonymized and kept under strict control, and (3) “genomic information or gene structures/functions possibly inherited by descendants” will not be analyzed.

15.13. Ethical Considerations

15.13.1. Informed consent

Informed consent from sample providers

The investigator will explain to the sample provider the significance, objective, methods, and expected results and risks of the study before enrollment using written information for patients and the informed consent form, and will obtain the freely given written consent of the sample provider. The investigator and sample provider will sign and date the informed consent form (date of informed consent discussion and date consent obtained). The written information for patients and informed consent form (copy) will be handed to the sample provider and the original will be stored with their medical records.

Items explained to the sample provider using the written information for patients and informed consent form

Before obtaining consent, the following items will be explained using the written information for patients and informed consent form.

- That participation in the study is voluntary. That there are no consequences of declining to participate.
- That patients can withdraw their consent to participate in the study at any time.
- That withdrawal of consent will have no impact on medical care.
- That samples will be disposed of when a patient withdraws their consent. That results of analysis will not be deleted if study results have already been published.
- The reason why the patient was selected to provide samples.
- The objective and methods of the study.
- Potential study results and potential risks faced by sample providers.
- That it is permissible to share information about the study plan and study methods.
- The types of documents the patient is required to provide and details about protection of personal information.
- That samples and genetic information will be provided to collaborating institutions.
- That results of gene expression analysis will not be disclosed.
- That intellectual property rights for this study do not belong to subjects.

15.13.2. Disclosure of analysis results

Because this study is an exploratory molecular biomedical study, the reproducibility of the data obtained must be validated in a clinical translational study and the data is not accurate or reliable enough to return to sample providers. Therefore, results of the analysis will not be disclosed to sample providers. Moreover, they will not receive genetic counseling because the mutations analyzed in this study are acquired somatic cell mutations. If the sample provider requests the data be disclosed, only the data from that sample provider will be explained in consideration of the above.

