15.1.8. Potential risks and discomforts

Peripheral blood samples (total of 12 mL) and a single tumor tissue specimen from normal liver biopsy (ultrasound-guided needle biopsy) will be analyzed in the translational study, and thus risks and discomforts associated with sample collection should be minimal. Risks related to patient rights and privacy are also very low because (1) the study will be conducted with the informed consent of the patient in accordance with the study protocol, (2) personal information will be anonymized and kept under strict control, (3) “genomic information or gene structures/functions possibly inherited by descendants” will not be analyzed, and (4) the genome of normal tissues will not be analyzed.

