It is now clear that copy number abnormalities and activating mutations in genes targeted by molecularly targeted cancer drugs are clinically effective biomarkers for those drugs. The importance of these biomarkers is widely recognized due to findings such as the effect of HER2 expression on trastuzumab, the effect of k-ras mutation on anti-EGFR antibody, and the effect of EGFR gene mutations on EGFR tyrosine kinase inhibitors. Specifically, identifying predictors of response to treatment with antineoplastic agents and stratifying treatment is not only advantageous because it reduces healthcare expenses, but also because it offers clear benefits for the patient such as avoiding adverse events from an ineffective drug and time wasted on ineffective treatment. The importance of biomarkers in predicting response to treatment with angiogenesis inhibitors is widely recognized by basic and clinical researchers alike, and is now the subject of much research. Some blood angiogenic proteins such as VEGF, tumor microvessel density, immunohistological assay of tumor angiogenic factors, and SNP of VEGFRs (the target molecules of multi-tyrosine kinase inhibitors) have also been investigated, but no clinically useful biomarker has been identified.

Two approaches were devised for this translational study. The goal of the first approach, which focuses on the effects of sorafenib as an angiogenesis inhibitor, is to measure the serum concentrations of multiple proteins that act as angiogenic factors and identify predictors of response and factors in drug resistance. The goal of the second approach, which focuses on the direct effect of sorafenib on hepatocellular carcinoma, is to analyze changes in cancer cell genome copy numbers and mutations in VEGFR2-like receptor families (e.g., VEGFRs, FGFRs, PDGFRs, and KIT) and BRAF, which are target molecules for sorafenib.

(1) Blood angiogenic factors and growth factors

Various cytokines, chemokines, and growth factors in blood, mainly VEGF, FGF, IL-8, IL-6, and TNF-alpha, are believed to be potent angiogenic factors.¹ Past studies relating to

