15.8.3. Measurement of cancer cell gene mutations

Mutations in VEGFR2-like receptor families (e.g., VEGFRs, FGFRs, PDGFRs, and KIT) and BRAF, which are target molecules for sorafenib, will be analyzed. Mutations in major oncogenes and tumor suppressor genes will also be investigated. The OncoCarta panel is an analytical technology based on time of flight mass spectrometry that can measure 239 mutations in 19 genes at once (See Translational Study Table 2). Gene mutations will also be detected by direct sequencing and correlations with response to treatment with sorafenib will be assessed.

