15.9. Biostatistical Analysis

Correlations between clinical data provided by the data center and various measured parameters will be analyzed at the Department of Genome Biology at Kindai University Faculty of Medicine and the Department of Medical Informatics at Niigata University Medical and Dental Hospital. Data on the degree of expression of quantified serum proteins,

gene copy numbers at about 250,000 loci in the cancer cell genome, and mutations in sorafenib target genes and major oncogenes will be obtained in this study. The following statistical methods will be used to analyze correlations between these measured data and clinical parameters. CGH analysis will be performed using Partek Genomic Suite 6.4 software (Partek Inc., St Louis, MO). Analysis of correlations of measured data with progression-free survival and overall survival will be performed using the Cox proportional hazards model. The clinical utility of factors as biomarkers will be evaluated by multivariate analysis with adjustment for clinical factors. In addition, differences in survival between subgroups will be compared with the log-rank test. Correlations between biomarkers and response rate will be assessed with Fisher's exact test. Statistical analysis will be performed and graphs created with SAS for Windows (ver. 9.1.3) or Medcalc for Windows (ver. 11.1.1).

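### The biomarker sub-study states as fact that only acquired mutations are analysed, but tumour DNA without patient-matched normal DNA cannot show that a variant is acquired

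*Protocol*

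**What the plan says.** Three statements in the Protocol describe what kind of genetic information the supplementary study handles.

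- Section 15.13.2 says of sample providers that "they will not receive genetic counseling because" "the mutations analyzed in this study are acquired somatic cell mutations". It also says that if a provider asks for disclosure, "only the data from that sample provider will be explained".
- Section 15.12 lists, among its reasons for calling the risk to rights and privacy very low, that "genomic information or gene structures/functions possibly inherited by descendants" will not be analysed.
- Section 15.1.8 gives the same reason and adds that "the genome of normal tissues will not be analyzed".

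The sampling and laboratory methods are set out elsewhere. Section 15.1.4 takes one tumour biopsy as the DNA source and aims to keep non-tumour tissue in it to a minimum. Blood is processed to serum for protein assays. Section 15.8.2 applies whole-genome CGH, and section 15.9 gives its scale: "gene copy numbers at about 250,000 loci in the cancer cell genome". Section 15.8.3 describes a fixed panel of 239 mutations in 19 genes and then adds: "Gene mutations will also be detected by direct sequencing and correlations with response to treatment with sorafenib will be assessed". Section 15.1.5 names somatic mutations as the target and makes mutation testing conditional on having enough DNA.

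**The concern.** A tumour cell carries the patient's inherited genome together with whatever the tumour has acquired. A method that reads tumour DNA beyond a list of predefined mutations therefore returns both kinds of difference. Without DNA from the same patient's normal tissue, the result does not show which is which. The Protocol states the acquired-only property as a fact and then draws conclusions from it.

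Two things are at stake.

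- **Interpretation.** Goals 2 and 3 in section 15.3 concern copy-number variations and mutations of the cancer cell. An inherited polymorphism or copy-number difference could enter the Cox, log-rank and Fisher analyses of section 15.9 and be reported as a tumour predictor.
- **What the ethics sections rest on.** The reason for no counselling and part of the very-low-risk statement depend on a property that the methods cannot demonstrate. Samples are linkable to the patient (15.7.6), genetic information goes to collaborating institutions (15.13.1), and a patient's own data may be explained on request (15.13.2).

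**Working it through.** No formula applies and the plan gives no figure to reproduce. The check sets the statements against the methods.

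1. **Source of DNA.** One biopsy of tumour tissue (15.1.4, 15.7.1). Non-tumour tissue is minimised, not excluded, so the extract may also contain DNA from normal cells.
2. **Patient-matched normal DNA.** None. Section 15.1.8 rules out analysis of the normal-tissue genome, and the blood samples serve protein measurement in serum (15.1.4, 15.7.3, 15.8.1). The exclusion of normal tissue is offered as a safeguard, but it also removes the comparator that would support the acquired-only claim.
3. **Copy number.** CGH compares the sample with a reference DNA, and the Protocol does not say which. A reference from another person leaves the patient's own inherited copy-number differences in the result. PCR verification (15.8.2) can confirm that a difference is present but not where it came from.
4. **Direct sequencing.** It reads whatever sequence is in the extract. Nothing in sections 15.8.3 or 15.9 classifies a call as inherited or acquired.
5. **Fixed panel.** It tests 239 predefined mutations in 19 genes, so it is the component least exposed.

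Comparison of claim and method:

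| Statement | What would secure it | What is planned |
|---|---|---|
| The mutations analysed are acquired (15.13.2) | Matched normal DNA, or assays confined to changes known to be acquired | Tumour DNA only; panel plus direct sequencing |
| Possibly inherited information is not analysed (15.1.8, 15.12) | Methods that do not read inherited sequence or copy number | Whole-genome CGH; direct sequencing where DNA suffices |

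**Number of patients.** Section 15.11 targets 80% to 90% of the main study, which plans 190 patients: 0.80 × 190 = 152 and 0.90 × 190 = 171. This is the enrolment target for the sub-study and so at most an upper range for those affected. Mutation testing depends on sufficient DNA, and the document gives no expected yield. The share of calls that would be inherited cannot be derived from the document, and no figure is offered here.

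**The case against.** The strongest reply is that the Protocol describes intent. Section 15.1.5 names somatic mutations as the target, and on that reading the later statements say what the study sets out to examine, not what tumour DNA contains. The inheritance phrase stands in quotation marks in sections 15.1.8 and 15.12, which suggests a category taken from a source not shown. Variant filtering is also commonly left to an analysis plan or a laboratory procedure. Section 15.13.2 itself calls the work exploratory and in need of validation. Finally, a variant that predicts response could stratify patients whatever its origin.

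Much of this stands. The intent is evidently somatic, the absence of a filter from the Protocol is not itself a fault, and a marker of inherited origin could still be useful. But intent is no means of achieving the property, and a filter kept elsewhere would lower the share of inherited calls without making the statements true. Section 15.13.2 asserts the property outright and gives it as the reason for a decision about patients.

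A reader might infer several stronger things that the document does not support:

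- **That there is no normal comparator at all.** CGH uses some reference; what is missing is a patient-matched one.
- **That all the named receptor genes and BRAF are directly sequenced.** Section 15.8.3 says mutations in those genes will be analysed but lists no genes for the sequencing step. Section 15.1.5 offers the panel or direct sequencing, if DNA suffices.
- **That every copy-number call feeds the biomarker tests.** Section 15.8.2 directs the correlations to sorafenib target genes and angiogenesis-related genes.
- **That the study will pursue inherited polymorphisms.** The background remark that "SNP of VEGFRs (the target molecules of multi-tyrosine kinase inhibitors) have also been investigated" refers to earlier work. It shows only that such polymorphisms are known in a gene family now to be analysed for mutations.
- **That patients are misinformed in the consent form.** The consent pages are not available to this review.

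**Conclusion.** The point holds: the acquired-only and nothing-inheritable statements are asserted, but the design does not secure them. It applies to direct sequencing and CGH, and least to the fixed panel. Its size in inherited calls is unknown.

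The conclusion rests on two premises: that tumour DNA includes the patient's inherited genome, and that no patient-matched normal DNA is analysed, which section 15.1.8 states. It does not depend on the identity of the CGH reference, unless that reference were the patient's own normal DNA, which section 15.1.8 excludes.

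The consequence is confined to how the exploratory biomarker results may be described and to the wording of the risk and disclosure sections. The overall survival comparison, its sample size and the randomisation are unaffected. The correction is worth making because it is cheap and changes both what the sub-study can claim and what its ethics sections rest on.

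**What to change.** - **Sections 15.1.8, 15.12 and 15.13.2.** Say that the study targets somatic changes, that tumour DNA also contains inherited sequence, and that without matched normal DNA the origin of a variant is not determined.
- **Section 15.13.2.** Reconcile the stated reason for no counselling with the sentence allowing a patient's own data to be explained on request. Which arrangement to adopt is for the investigators and ethics committees.
- **Sections 15.8.2, 15.8.3 and 15.9.** Remove known population polymorphisms and common inherited copy-number regions before the correlation tests. Report the remaining non-panel calls as of undetermined origin, not as cancer-cell mutations or copy-number variations.
- **Keep the scope of the mutation analysis.** Restricting it to the fixed panel would be simpler but could drop sorafenib-target genes named in section 15.8.3. The part of the panel list available here shows no VEGFR entry, though that list is incomplete.

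The cost is a filtering step and some rewording, with no new sample. There will be fewer reportable variants and weaker tumour-specific claims, and filtering will not remove rare inherited variants, which is why the label is still needed. Adding matched normal DNA would address origin directly, but it would need further samples and a change to the exclusion of normal tissue in section 15.1.8.

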15.14. Data Collection

Clinical data that can be obtained in the main study, for example, data on treatment efficacy, will be used in this study. Clinical data and sample storage charts (with translational study sample numbers and storage locations recorded at the time of storage) will be stored at the SILIUS-TR data center.

15.17. Publication of Study Results

Investigators, the study coordinator, or collaborating researchers will compile study results as soon as possible and determine whether to file a patent application. The applicant and the inventor will be determined separately considering the facts of the matter. The results will be published in a suitable English-language journal or presented at a conference. Co-authors will be only those who reviewed the manuscript before submission and agreed to presentation contents.

G464R, G464VE, G466R, F468C, G469S, G469E, G469A, G469V, G469R, G469R, D594VG, F595L, G596R, L597S, L597R, L597Q, L597V, T599I, V600E, V600K, V600R, V600L, K601N, K601E

CDK

R24C, R24H

EGFR

R108K, T263P, A289V, G598V, E709K/H, E709A/G/V, G719S/C, G719A, M766_A767insAI, S768I, V769_D770insASV, V769_D770insCV, D770_N771>AGGN769_D770insASVV769_D770insASV, D770_N771insG, N771_P772>SVDNR, P772_H773insV, H773>NPY, H773_V774insNPH/PH/H, V774_C775insHV, T790M, L858R, L861Q, E746_T751del, E746_A750del, E746_T751del, E746_T751del, S752D, L747_E749del, L747_T750del, L747_S752del, L747_T751del, L747_S752del, P753S, A750P, T751A, T751P, T751I, S752W/F, S752_I759del, L747_Q ins, E746_T751del, I ins (combined), E746_A750del, T751A (combined), L747_E749del, A750P (combined), L747_T750del, P ins (combined), L747_S752del, Q ins (combined)

ERBB2

L755P, G776S/LC, G776V/C, A775_G776insYVMA, P780_Y781insGSP, P780_Y781insGSP, S779_P780insVGS

FGFR1;FGFR3

S125L, P252T; G370C, Y373C, A391E, K650Q/E, K650T/M

FLT3

I836del, D835H/Y

17. PUBLICATION OF STUDY RESULTS

After the end of the study, the research group will compile the results as soon as possible and publish them in a suitable English-language journal and present them at conferences. Co-authors will be determined by degree of contribution to the study (e.g., number of

patients enrolled, participation in biomarker analysis, and participation in statistical analysis) and by discussion, up to the maximum number allowed by the journal in which results are to be published.

18. CLINICAL TRIAL REGISTRATION

This study will be registered in a public database and information made public until the first patient is enrolled.

19. PROTOCOL REVISION HISTORY

Ver.1	Data	17/07/2010
Ver.1.1	Data	27/07/2010
Ver.1.2	Data	03/08/2010
Ver.1.3	Data	30/08/2010
Ver.1.4	Data	17/09/2010
Ver.1.5	Data	07/10/2010
Ver.1.6	Data	19/10/2010
Ver.2.0	Data	14/02/2011
Ver.2.1	Data	15/09/2012
Ver.2.2	Data	20/09/2013
Ver.2.3	Data	06/06/2015

21. REFERENCE MATERIALS

21.1. Child-Pugh Score

	Point score calculated from observations		
	1	2	3
Grade of encephalopathy ^a	Absent	1-2	3-4
Ascites	Absent	Slight	Moderate
Serum bilirubin (mg/dL)	< 2	2-3	> 3.0
(mcmol/L)	< 34	34-50	> 50
Serum albumin (g/dL)	> 3.5	2.8-3.5	< 2.8
INR	< 1.7	1.7-2.3	> 2.3
Prothrombin time (sec above normal)	< 4	4-6	> 6
Increase in prothrombin time (%)	> 70	40-70	< 40

b Grade of encephalopathy:

Grade 0: Lucid, normal personality, normal neurological test results, normal electroencephalogram

Grade 1: Restlessness, sleep disorder, irritability/agitation, tremors, dysgraphia, 5 cps waves

Grade 2: Lethargy, disorientation (temporal), inappropriateness, difficulty maintaining stable posture, ataxia, slow triphasic waves

Grade 3: Somnolence, confusional state, disorientation (spatial), hyperreflexia, rigidity, slow waves

Grade 4: Coma, no personality/unresponsive, cessation of cerebral activity, slow 2-3 cps delta activity

A: 5-6 points, B: 7-9 points, C: 10-15 points

*Ascites: Patients with a history of ascites who are currently using a diuretic are given 2 points even if they do not have ascites.

*Encephalopathy: Patients with a history of hepatic encephalopathy who are using a drug to treat encephalopathy are given 2 points even if they are asymptomatic.

21.2. Eastern Cooperative Oncology Group (ECOG) PS

Grade	Definition
0	Fully active, able to carry on all pre-disease performance without restriction.
1	Restricted in physically strenuous activity, but ambulatory and able to carry out work of a light or sedentary nature (e.g., light house work or office work).
2	Ambulatory and capable of all selfcare but unable to carry out any work activities. Up and about

	more than 50% of waking hours.
3	Capable of only limited selfcare, confined to bed or chair more than 50% of waking hours.
4	Completely disabled. Cannot carry on any selfcare. Totally confined to bed or chair.

21.3. Staging by the General Rules for the Clinical and Pathological Study of Primary Liver Cancer

The overall stage of a cancer is determined by calculating stages for each component and selecting the highest one.

[figure not shown]
[figure not shown]

[figure not shown]

[figure not shown]

[figure not shown]

The overall stage is determined from the following four components.

Stages of hepatocellular carcinoma

	T component	N component	M component
Stage I	T1	N0	M0
Stage II	T2	N0	M0
Stage III	T3	N0	M0
Stage IVA	T4	N0	M0
	T1, T2, T3, T4	N1	M0
Stage IVB	T1, T2, T3, T4	N0, N1	M1

T component: Determined from three factors: the number, size, and vascular invasion of tumors. Multiple tumors can be multicentric tumors or intrahepatic metastases. An S3 ruptured hepatocellular carcinoma is classified as T4.

T component of hepatocellular carcinoma

	T1	T2	T3	T4
① Number of tumors: Single	Meets all (1) (2) (3)	Meets 2	Meets 1	Meets none
(2) Tumor diameter: ≤ 2 cm		 	 	
(3) No vascular invasion (Vp0, Vv0, B0)		 	 	

N component:

N0: No lymph node metastasis

N1: Lymph node metastasis

M component:

M0: No extrahepatic spread

M1: Extrahepatic spread

